4.10 Immunogenicity

For Part A (SAD) and Part B (MAD) (separately and combined), immunogenicity summaries will be provided by treatment group on ATAS. Subjects with any ADA positive samples, screening (ADA status) and confirmatory assay (titer and ADA status) results will be included. The results for 3-Tiers will be displayed. If the sample is ADA-positive then the reactivity to the CCI will be included.

A by-subject listing of immunogenicity will be provided by study part and treatment group on enrolled subjects.

CCI

CCI

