Clinical Procedures						
Physical Examination	X ³					X
Pregnancy Test ⁴	X	X ⁵				
Vital Signs ⁶	X	X ⁵		X		
Con Meds/Procedures, Incidental Gluten Exposure	X	X	X	X	X	X
Safety Assessments						
Adverse Events	X	X ⁷	X	X	X	X
Lab Tests (Safety)	X	X ⁵	X	X		X
Study Drug Administration						
KAN-101 Administration		X				
Additional Blood Samples						
PK Blood Sample		X ⁸				
ADA Serum Sample		X ⁵			X	X

¹ All patients will be assessed via central laboratory for HLA genotype and CeD serology (eg, tTG-IgA and DGP-IgG) at screening to confirm eligibility. For rescreening, HLA does not need to be repeated and CeD serology only needs to be repeated if >3months have elapsed from last assessment.

² ECG performed pre dose (at least 5 min before infusion), 20(±5) min after start of infusion, and 1 hour (±10 min) post infusion

- ³ Includes weight and height at screening only.
- ⁴ Pregnancy test at screening must be serum; serum or urine tests are acceptable on D1 prior to dosing.
Pregnancy test must be negative before study drug is administered.
- ⁵ Samples/Measurements taken pre-dose (at least 5 min prior to infusion).
- ⁶ Vital signs (pulse rate, temperature, diastolic and systolic BP).
- ⁷ On D1 patients will be observed in the clinic/hospital unit for 10 h after initiation of IV infusion and followed up with by phone approximately 24 hours after dosing.
- ⁸ PK samples to be taken pre-dose (at least 5 min prior to infusion) and the following timepoints after the end of infusion: 0 (+2) min, 7 (\pm 2) min, 15 (\pm 2) min, 30 (\pm 5) min, 1 h (\pm 5 min), 2 h (\pm 5 min), 3 h (\pm 5 min), 4 h (\pm 5 min) and 6 h (\pm 5 min).

Abbreviations: ADA = anti-drug antibody; BB = blood pressure; CeD = celiac disease; Con Meds = concomitant medications; ECG = electrocardiogram; Early Term. = early termination; HBV = hepatitis B; HCV = hepatitis C; HIV = human immunodeficiency virus; HLA = Human Leukocyte Antigen; PK = pharmacokinetics; SAD = single ascending dose.

Table 2: Schedule of Assessments Part B (MAD)

Assessments	Screening	Treatment Period			PD Assessment		Follow-up ¹	Early Term.
		1	4	7	15	21		
Study Day	-28	1	4	7	15	21	28 (±3)	
Screening Assessments								
Informed Consent	X							
Medical History & Demographics	X							
Disease History	X							
Inclusion/Exclusion	X							
ECG	X	X ²		X ²	X ¹⁵			
HIV, HBV, HCV testing	X							
HLA Genotype and CeD Serology ³	X							
Clinical Procedures								
Physical Exam	X ⁴							X
Pregnancy Test ⁵	X	X ⁶	X ⁶	X ⁶				

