1.2. KAN-101

KAN-101 is composed of a synthetic liver-targeting glycopolymer that is conjugated to a synthetic **CC1** peptide domain of wheat alpha gliadin (KAN0009) recognized by the HLA-DQ2.5 haplotype. KAN0009 does not bind to the HLA DQ8 molecule. KAN-101 is a liquid formulation drug product administered parenterally via an intravenous (IV) infusion.

KAN-101 harnesses natural tolerogenic pathways in the liver (Thomson 2010) to reprogram pathogenic immune cells to become tolerant toward specific antigens. KAN-101 specifically targets the immune cells that drive CeD and leaves the otherwise healthy components of the immune system intact to perform their natural, protective functions. The mechanism by which KAN-101 induces immunologic tolerance is mediated by 3 mechanisms:

- Deletion of antigen-specific T cells
- Induction of anergy/clonal exhaustion of antigen-specific T cells
- Induction of regulatory T cells which control the antigen-specific T-cell response

In nonclinical mouse models and a non-human primate model, administration of surrogate molecules of KAN-101 were effective at inducing T-cell tolerance. From these nonclinical models, it was concluded:

- Three doses of surrogate molecules administered every 3 days was significantly more effective in inducing tolerance and improving disease outcome compared to 3 doses administered weekly.
- The doses where optimal efficacy was observed for the surrogate molecules in nonclinical models is equivalent to 1.5 to 7.0 mg/kg of KAN-101. Doses of surrogate molecules equivalent to 0.3 mg/kg of KAN-101 have demonstrated effects on disease severity in nonclinical models.
- T-cell tolerance induction can be observed as early as 1 week after drug administration in nonclinical models, supporting the observational period for the dosing of the sentinel patients across cohorts.

Previous clinical studies using an adjuvant-free mix of 3 peptides were able to induce T-cell tolerance in patients with CeD (Goel 2017). Intradermal administration of these non-targeted peptides induced moderate celiac-like GI symptoms in some patients, including nausea, abdominal pain, and vomiting, with onset within hours of drug administration. In general, these symptoms are consistent with symptoms experienced by CeD patients after ingestion of gluten (Goel 2017).

For more information on the nonclinical findings, please see the KAN-101 Investigator's Brochure.

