5. STUDY POPULATION

5.1. Inclusion Criteria

1. Adults aged 18 to 70 years inclusive
2. Diagnosed with CeD based on positive serology (eg, tissue transglutaminase IgA antibody [tTG-IgA] and/or deamidated gliadin peptide IgG [DGP-IgG]) and intestinal histology consistent with \geq Marsh Type II or with evidence of villous atrophy
3. Has HLA-DQ2.5 genotype (*HLA-DQA1*05* and *HLA-DQB1*02*) (homozygotes or heterozygotes)
4. Has followed a GFD for > 12 months immediately prior to study entry
5. Negative or weak positive for tTG IgA and negative or weak positive for DGP-IgA/IgG during screening
6. Male or female. Females of childbearing potential must use at least 2 acceptable birth control methods
7. Capable of understanding and complying with protocol requirements
8. Patient understands and has signed the informed consent form (ICF)

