3.5.3 Immunogenicity Assessments

Anti-drug antibody (ADA) sampling will be performed at the time points shown in Appendix 6.1 Table 8 (Part A) and Table 9 (Part B). ADA-positive or ADA-negative will be determined for each time point. If the first test comes back positive then the reactivity to the CCI

CCI [REDACTED] will be assessed separately. Titers will be determined for ADA positive sample if the quantity is sufficient for the determination. If Screening tier is Negative then ADA response is Negative at the corresponding visit. If Screening tier is Positive then ADA response is Confirmatory Tier response (Positive, Negative or QNS (quantity not sufficient) at the corresponding visit.

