5. Pregnancy test at screening must be serum; serum or urine tests are acceptable predose on D1, D4, and D7. Pregnancy test must be negative before each dose of study drug is administered.
6. Samples/Measurements taken pre-dose (at least 5 min prior to infusion).
7. Vital signs (pulse rate, temperature, diastolic and systolic BP).
8. The GC will consist of patients self-administering 9 g of gluten protein PO for each of 3 days (D15 to D17), with the first administration in the clinic on D15. GC should be administered at approximately the same time each day.

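### The SAP defines no treatment-emergent ADA, so its any-positive summary by dose mixes antibodies present before dosing with those first seen after it

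*SAP*

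**What the plan says.** SAP 4.10 provides immunogenicity summaries by treatment group on the All Treated Analysis Set, for Parts A and B separately and combined. The count it names is "Subjects with any ADA positive samples", and the full sentence on content reads: "Subjects with any ADA positive samples, screening (ADA status) and confirmatory assay (titer and ADA status) results will be included". It also displays the results of the three assay tiers and adds a by-subject listing. In that sentence, screening means the first assay tier, not the screening visit.

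SAP 3.5.3 refers to the schedules in Appendix 6.1 for sampling times and states that "ADA-positive or ADA-negative will be determined for each time point". Titers are determined for positive samples when enough material remains.

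In SAP Tables 8 and 9 (Protocol Tables 1 and 2), ADA is sampled on D1, on D21 and at early termination. The D1 entry carries the footnote "Samples/Measurements taken pre-dose (at least 5 min prior to infusion". In Part B, D21 falls after the gluten challenge of D15 to D17; Part A has no challenge.

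SAP 4 lists pooled placebo among the Part B reporting groups for everything except PK. SAP 4.3.1 defines baseline for non-PK outputs as the last pre-treatment assessment, and SAP 3.5.1.1 defines treatment-emergent for adverse events. The visible text applies neither idea to ADA.

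**The concern.** An ADA table by dose is normally read to learn whether the drug provokes antibodies. A pre-dose sample cannot answer that, yet here it is one of two scheduled samples and is enough to place a subject in the any-positive count.

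Pre-dose reactivity is plausible in this population. Protocol 1.2 describes the peptide part of KAN-101 as a domain of "wheat alpha gliadin (KAN0009) recognized by the HLA-DQ2.5 haplotype". Protocol 5.1 requires positive celiac serology at diagnosis and admits patients who are "negative or weak positive for DGP-IgA/IgG during screening"; Protocol 6.1.8 sets that limit at below 30 U/mL. The documents do not show that such antibodies react in the ADA assay, so this is a reason for care and not evidence of a rate.

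At stake is how the by-dose immunogenicity result is interpreted in groups of 3 to 6 subjects. A second issue is timing: without a rule for a meaningful titer rise over baseline, deciding whether a pre-dose positive was boosted would be left until the data are seen, although SAP 1 places analysis decisions before database lock.

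**Working it through.** The plan states no ADA rate and no prevalence of pre-existing ADA, so there is no figure to reproduce. The check is textual, followed by an illustration of size.

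**Text**
1. Counting rule (SAP 4.10): any positive sample, with no restriction on timing.
2. Samples (SAP Tables 8 and 9): D1 pre-dose, D21, early termination.
3. From 1 and 2, a subject positive on D1 pre-dose and negative on D21 meets the any-positive rule.
4. Baseline-referenced rule for ADA: none in visible SAP 3.5.3, 4.3.1 or 4.10.

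**Weight of one pre-dose positive**
Group sizes are from SAP 3.2: 3 or 6 per Part A cohort and 6 active per Part B cohort.
- Group of 6: 1/6 = 16.7 points.
- Group of 3: 1/3 = 33.3 points.
- Parts combined at a common dose: 3 + 6 = 9 to 6 + 6 = 12 subjects, so 1/9 = 11.1 down to 1/12 = 8.3 points.

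**Chance of at least one pre-dose positive in a group**
This is 1 − (1 − q)^n, where q is the pre-existing prevalence. The range for q is an assumption.

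| q (assumed) | n = 3 | n = 6 |
|---|---|---|
| 2% | 6% | 11% |
| 5% | 14% | 26% |
| 10% | 27% | 47% |
| 20% | 49% | 74% |

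For example, with n = 6: 1 − 0.98^6 = 0.114 and 1 − 0.80^6 = 0.738.

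**Effect on the expected rate**
Let t be the proportion of baseline-negative subjects who turn positive after dosing. The expected any-positive rate is q + (1 − q)t.
- t = 0: the any-positive rate is q, that is 2% to 20%; a count of baseline-negative subjects turning positive gives 0%.
- t = 10%: 0.02 + 0.98 × 0.10 = 11.8%, up to 0.20 + 0.80 × 0.10 = 28%; the baseline-negative count gives 10%.

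**The case against.** A reader might infer that the SAP reports pre-existing antibodies as though KAN-101 had induced them. The documents do not support that. SAP 4.10 is descriptive, attributes nothing to the drug and names no headline incidence. Status is held per time point and listed by subject, so with one scheduled sample before dosing and one after, a reader can see who was positive beforehand. This stands. It limits the harm, but a listing does not set the figure shown by dose, and it supplies no rule for boosted responses.

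A reader might also infer that positivity after the gluten challenge cannot be judged because placebo is not shown on the same terms. That fails too: pooled placebo is already a Part B reporting group, its patients take the same challenge (Protocol 6.1.11), and they have the same ADA samples. What remains is that with only 6 placebo patients, a chance imbalance in pre-dose positivity can blur the comparison if the count is any-positive.

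Three further points stand. The assumed prevalence has no source in the documents. Parts of SAP 3.5.3 and 4.10 are redacted and the table shells are a separate document, so a baseline split there cannot be excluded. ADA appears in no visible objective or endpoint, and the study tests no hypotheses.

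**Conclusion.** The concern holds in a limited form. The only counting rule visible in SAP 4.10 includes the D1 pre-dose sample, and no visible text defines treatment-emergent ADA, so the by-dose summary mixes pre-existing and post-dose positivity. The shift per subject, about 17 points in a group of 6 and 33 in a group of 3, follows from the planned group sizes. How often it would occur is unknown: the 11% to 74% for a group of 6 rests wholly on the assumed 2% to 20% prevalence and on subjects being independent.

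This affects the reading of a descriptive safety table. It does not touch the primary or secondary endpoints, and it does not show that the plan credits pre-existing antibodies to the drug. It is worth correcting because the remedy is cheap and uses data already planned.

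**What to change.** In SAP 4.10, report by treatment group, including the existing pooled placebo column in Part B:
- baseline-positive: positive in the confirmatory tier on the D1 pre-dose sample;
- treatment-induced: negative pre-dose and confirmed positive at any post-dose sample;
- treatment-boosted, where titers are available: positive pre-dose with a titer rise over baseline by a factor fixed before database lock.

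Use as denominator the subjects with a baseline and at least one post-dose ADA result, and show that number. Keep any-positive as a secondary row.

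The cost is one definition paragraph and a few table rows. The limitation is that titers depend on sample quantity (SAP 3.5.3), so boosted status may be undeterminable for some baseline-positive subjects; count these separately rather than as not boosted.

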4.12 Disposition of Subjects and Screen Failures

A clear accounting of the disposition of all subjects who enter the study will be provided, from screening to end of study participation. Number and percentage of subjects screened, enrolled/randomized, subjects completed treatment, subjects discontinued from the study and discontinuation reasons (including reasons for early withdrawal).

For Part A and Part B (separately and combined), summary tables will be provided by treatment group for subject disposition on enrolled subjects.

Listing will consist of ICF date, enrollment details (last contact date, reason of screened failure), randomization codes, visit dates, and withdrawal details (including reason for discontinuation and duration of treatment prior to discontinuation).

A by-subject listing will be provided by study part and treatment group for study treatment / randomization codes, study drug completion status, study completion status and subject disposition will be on enrolled subjects. Screen failures, and subjects who did not meet study eligibility criteria listings will be on listing of screened subjects.

4.13 Demographics and Baseline Celiac Disease Characteristics

For summary table, continuous and categorical demographic characteristics (age, sex, race, ethnicity; height and weight at Screening; and body mass index (BMI) derived) will be provided.

For Part A and Part B (separately and combined), summary tables will be provided by treatment group for demographics on ATAS.

The summary table will contain continuous and categorical celiac disease specific baseline characteristics (example years since first CeD diagnosis, number of years on GFD) will be provided by treatment group.

For Part A and Part B (separately and combined), summary tables will be provided by treatment group for baseline celiac disease characteristics on ATAS.

A by-subject listing will be provided by study part and treatment group for demographics and baseline celiac disease characteristics on enrolled subjects.

4.14 Medical History

All medical history will be coded using Version 23.1 or higher of the Medical Dictionary for Regulatory Activities (MedDRA).

For Part A (SAD) and Part B (MAD) separately, summary tables will be provided by treatment group for Medical History on ATAS.

Listings will include start and stop dates.

A by-subject listing will be provided by study part and treatment group for medical history on enrolled subjects.

[figure not shown]
CCI

CCI

[figure not shown]
CCI

CCI

CCI

CCI

5 REFERENCES

- [1] SAS® Version 9.4 of the SAS System for Personal Computers. Copyright © 2002-2003. SAS Institute Inc. SAS and all other SAS Institute Inc. product or service names are registered trademarks or trademarks of SAS Institute Inc., Cary, NC, USA.
- [2] Phoenix®WinNonlin® Professional Software Version 8.0. <https://www.certara.com>

6 APPENDICES**6.1 Schedule of Assessments****Table 8: Schedule of Assessments Part A (SAD)**

Assessment	Screening	Study Period				Early Term.
		1	4 (± 1)	8	D21 (± 1)	
Study Day	-28	1	4 (± 1)	8	D21 (± 1)	
Screening Assessments						
Informed Consent	X					
Medical History & Demographics	X					
Disease History	X					
Inclusion/Exclusion	X					
ECG	X	X ²		X		
HIV, HBV, HCV testing	X					
HLA Genotype and CeD Serology ¹	X					
Clinical Procedures						
Physical Examination	X ³					X
Pregnancy Test ⁴	X	X ⁵				
Vital Signs ⁶	X	X ⁵		X		
Con Meds/Procedures, Incidental Gluten Exposure	X	X	X	X	X	X
Safety Assessments						
Adverse Events	X	X ⁷	X	X	X	X
Lab Tests (Safety)	X	X ⁵	X	X		X
Study Drug Administration						
KAN-101 Administration		X				
Additional Blood Samples						
PK Blood Sample		X ⁸				
ADA Serum Sample		X ⁵			X	X

 All patients will be assessed via central laboratory for HLA genotype and CeD serology (eg, tTG-IgA and DGP-IgG) at screening to confirm eligibility. For rescreening, HLA does not need to be repeated and CeD serology only needs to be repeated if >3months have elapsed from last assessment. ECG performed pre dose (at least 5 min before infusion), 20(± 5) min after start of infusion, and 1 hour (± 10 min) post infusion. Includes weight and height at screening only. Pregnancy test at screening must be serum; serum or urine tests are acceptable on D1 prior to dosing. Pregnancy test must be negative before study drug is administered. Samples/Measurements taken pre-dose (at least 5 min prior to infusion). 						

Assessment	Screening	Study Period				Early Term.
Study Day	-28	1	4 (±1)	8	D21 (±1)	

6. Vital signs (pulse rate, temperature, diastolic and systolic BP).
 
7. On D1 patients will be observed in the clinic/hospital unit for 10 h after initiation of IV infusion and followed up with by phone approximately 24 hours after dosing.
 
8. PK samples to be taken pre-dose (at least 5 min prior to infusion) and the following timepoints after the end of infusion: 0 (+2) min, 7 (±2) min, 15 (±2) min, 30 (±5) min, 1 h (±5) min, 2 h (±5 min), 3 h (±5 min), 4 h (±5 min), 6 h (±5 min).
						

Abbreviations: ADA = anti-drug antibodies; BP = blood pressure; CeD = celiac disease; Con Meds = concomitant medications; ECG = electrocardiogram; Early Term. = early termination; HBV = hepatitis B; HCV = hepatitis C; HIV = human immunodeficiency virus; HLA = Human Leukocyte Antigen; PK = pharmacokinetics; SAD = single ascending dose.
						

Table 9: Schedule of Assessments Part B (MAD)

Assessments	Screening	Treatment Period			PD Assessment		Follow-up ¹	Early Term.
		1	4	7	15	21		
Study Day	-28	1	4	7	15	21	28 (±3)	
Screening Assessments								
Informed Consent	X							
Medical History & Demographics	X							
Disease History	X							
Inclusion/Exclusion	X							
ECG	X	X ²		X ²	X ¹⁵			
HIV, HBV, HCV testing	X							
HLA Genotype and CeD Serology ³	X							
Clinical Procedures								
Physical Exam	X ⁴							X
Pregnancy Test ⁵	X	X ⁶	X ⁶	X ⁶				
Vital Signs ⁷	X	X ⁶			X			
Con Meds/Procedures, Incidental Gluten Exposure	X	X	X	X	X	X	X	X
3-Day GC					X ⁸			
Safety Assessments								
Adverse Events	X	X ¹⁰	X ¹⁰	X ¹⁰	X	X	X	X
Lab Tests (Safety)	X	X ⁶	X ⁶	X ⁶	X			X
Study Drug Administration								
KAN-101/PBO Administration		X	X	X				
Additional Blood Samples								
PK Blood Sample		X ¹¹	X ⁶	X ¹²	X ¹⁵			
ADA Sample		X ⁶				X		X

CCI

CCI

Assessments	Screening	Treatment Period			PD Assessment		Follow-up ¹	Early Term.
		1	4	7	15	21		
Study Day	-28	1	4	7	15	21	28 (±3)	

CC [REDACTED]

1. Phone call.
2. ECG performed pre dose (at least 5 min before infusion), 20(±5) min after start of infusion, and 1 hour (±10 min) post infusion.
3. All patients will be assessed via central laboratory for HLA genotype and CeD serology (eg, tTG-IgA and DGP IgG) at screening to confirm eligibility. For rescreening, HLA does not need to be repeated and CeD serology only needs to be repeated if >3months have elapsed from last assessment.
4. Includes weight and height at screening only.
5. Pregnancy test at screening must be serum; serum or urine tests are acceptable predose on D1, D4, and D7. Pregnancy test must be negative before each dose of study drug is administered.
6. Samples/Measurements taken pre-dose (at least 5 min prior to infusion).
7. Vital signs (pulse rate, temperature, diastolic and systolic BP).
8. The GC will consist of patients self-administering 9 g of gluten protein PO for each of 3 days (D15 to D17), with the first administration in the clinic on D15. GC should be administered at approximately the same time each day.
9. CC [REDACTED]
10. On D1 patients will be observed in-clinic for 10 h from the start of IV infusion and followed up with by phone approximately 24 hours after dosing; on D4 and D7 (dosing days) patients will be observed for 4 h in clinic from the start of IV infusion.
11. PK samples to be taken at pre-dose (at least 5 min prior to infusion) and the following timepoints after the end of infusion: 0 (+2) min, 7 (±2) min, 15 (±2) min, 30 (±5) min, 1 h (±5 min), 2 h (±5 min), 3 h (±5 min), 4 h (±5 min), 6 h (±5 min).
12. PK samples to be taken at pre-dose (at least 5 min prior to infusion) and the following timepoints after the end of infusion :0 (+2) min, 7 (±2) min, 15 (±2) min, 30 (±5) min, 1 h (±5 min), 2 h (±5 min), and 4 h (±5 min).
13. CC [REDACTED]
14. CC [REDACTED]
15. Collected prior to oral gluten challenge.

Abbreviations: ADA = anti-drug antibodies; BP = blood pressure; CC [REDACTED] CeD = celiac disease; Con Meds = concomitant medications; Early Term = early termination; ECG = electrocardiogram; CC [REDACTED] GC = gluten challenge; HBV = hepatitis B; HCV = hepatitis C; HIV = human immunodeficiency virus; HLA = Human Leukocyte Antigen; IV = intravenous; MAD = multiple ascending dose; CC [REDACTED] PBO = placebo; PD = pharmacodynamics; PK = pharmacokinetics; CC [REDACTED]

CCI

CCI

CCI

CCI

CCI

PPD
